9.1. Screening + Baseline Phase

The screening + baseline phase may not exceed 28 days (4 weeks), with the exception of delays caused by scheduling issues, see [Section 6.4](#)). The length of the screening visit for a given individual subject will be determined by the requirement to discontinue all drugs used to treat MF at least 7 days prior to the first baseline evaluation (ie, must discontinue prior MF therapy by Day -14). Subjects who are not currently taking any drugs to treat their MF may complete all screening activities in a few days, and proceed to the baseline phase.

9.1.1. Screening Assessments

Prospective participants will be scheduled for a screening visit by site staff. A subject number will be assigned by an Interactive Voice Response System (IVRS). All procedures for screening and baseline must be completed within the 21-day screening + 7-day baseline phase, except as noted in [Section 6.4](#). The following procedures will be performed:

Obtain informed consent before any study specific procedures are conducted.

- A subject number will be assigned by IVRS.
- Review of eligibility criteria including discussion of methods known to be at least 99% effective in preventing pregnancy ([Appendix 3](#)).
- Review of medical history, prior medication history and prior history of medications used to treat MF (see [Section 8.8](#), Prior and Concomitant Medications). Record medication histories on the eCRF.
- Review of transfusion history. Complete transfusion history should be recorded where possible, but must include at least the 12 weeks prior to Screening. The history should be recorded on the eCRF.
- Confirm that all drugs, used to treat underlying MF disease will be discontinued by Day -14, so that at least 1 week will have elapsed between the last dose of medication(s) used to treat MF and the baseline MRI (or CT scan in applicable subjects) and diary dispensing. Prior MF medication(s) may be discontinued in one of the 3 following ways:
 1. Prior to and independent of considering enrollment in this study (prior to signing the ICF). These subjects can proceed to the baseline visit as soon as screening activities are completed, 7 days have elapsed since the prior MF medications were discontinued and eligibility is verified.
 2. At the time of signing the ICF. These subjects can proceed to the baseline visit 7 days after signing the ICF, if screening activities are completed and eligibility is verified.
 3. After confirming eligibility via the screening symptom form, laboratory assessments, and medical history. These subjects must obtain necessary screening visit results within the first 14 days in order to have 7 days for drug discontinuation prior to baseline (total screening time elapsed = 21 days).

- NOTE: The timing for the screening hematology blood samples should take the possible discontinuation of a prior MF therapy into account, in order to allow time for possible recovery of low platelet count values caused by the prior MF regimen. It is suggested that the hematology blood sample be taken around Day -8, eg, at the end of the possible wash-out period for prior therapy.
- Complete Screening Symptom Form.
- Record adverse events.
- Comprehensive physical examination including body weight and height.
- Measurement of spleen length below the costal margin by palpation.
- Vital signs
- ECOG status assessment.
- 12-lead electrocardiogram (ECG).
- Bone marrow biopsy for confirmation of MF diagnosis. NOTE: a bone marrow biopsy at screening or baseline is required if a biopsy was not previously obtained within the prior 2 months or if all data from the samples are not available for review by the Study Investigator of Study INCB 18424-258. The prior data will need to be entered into the eCRF for this study, with explanation as to the origin of the data (date of biopsy).
- Blood sampling for the following laboratory tests (see [Appendix 4](#)):
 - Serum chemistry tests
 - Hematology
 - Coagulation tests
 - Serum pregnancy test (females of childbearing potential only)
 - Serology tests for HIV and hepatitis

9.1.2. Baseline Assessments

The results from the screening visit evaluations will be reviewed to determine if the subject continues to meet the eligibility requirements as specified in the protocol. Subjects who have signed the ICF and meet all the entry criteria (see [Section 6](#)) may be enrolled in the study, and will be contacted by clinical site staff to schedule the baseline visit. Subjects will be reminded by site staff that they must arrive for the baseline visit where blood draws for lipid profile will be taken after an overnight fast of at least 8 hours or since midnight.

Subjects will begin completing the evening diary the evening of the first baseline assessment (Day -7). The MRI (or CT scan in applicable subjects) should be conducted on the first or second day to allow ample time for the central imaging laboratory to verify scan quality. Blood samples for hematology and serum chemistry should be taken as close as possible to Day 1, but in ample time for the results to be returned from the central laboratory (or in the case of

hematology and coagulation labs, the local laboratory). If, on the baseline assessment of serum chemistry and hematology parameters, an exclusionary value is observed, the test may be repeated once, no more than 3 days following the first observation.

The following procedures will be performed during the 7-day baseline period and prior to enrollment for all subjects:

- Confirm that the subject continues to meet all eligibility criteria.
- Update medication history and concurrent medications; confirm that all drugs used to treat underlying MF disease have been discontinued for at least 7 days.
- Update transfusion history status.
- Record adverse events.
- Conduct a comprehensive physical examination.
- Measurement of spleen length below the costal margin by palpation.
- Vital signs.
- ECOG status assessment.

█ [REDACTED]

- Bone marrow biopsy (only if not performed at screening and no prior biopsy data are available to the Investigator for review).
- Blood sampling for the following laboratory tests (see [Appendix 4](#)):
 - Serum chemistry tests
 - Hematology
 - Coagulation tests
 - Lipid panel

█ [REDACTED]

█ [REDACTED]

█ [REDACTED]

- MRI of the upper and lower abdomen and pelvis will be performed, to assess spleen volumes. CT scan may be performed if subject is not a candidate for MRI, or if MRI is not readily available. The MRI (or CT scan in applicable subjects) should be performed on the first or second day of the baseline period (ie, Day -7 or Day -6), and the site radiologist should send the scan to the central imaging laboratory that same day. Scans can be sent by file transfer protocol (ftp) or by mailing it on a CD-ROM by pre-paid mailer provided for the study. The MRI central reader will assess the quality of the scan and will send a notice of acceptance via FAX and/or email to the site within 48 hours of receipt of the scan at their offices. A notice of acceptance MUST be received by the site before the subject can begin dosing. If a notice of “non-acceptance” is received by the investigator, the subject must have a repeat MRI (or CT in applicable subjects) prior to

receiving the first dose of study drug. This MRI should be performed within 2 weeks of the first MRI. In rare cases, the central imaging laboratory may suggest that CT scan be performed instead of MRI because of subject's abdominal anatomy.

- NOTE: the first MRI may be delayed for up to 2 weeks because of scheduling or other issues at the clinic site, but must be completed within 56 days, maximum from the start of the original screening visit date, and this must occur prior to the subject receiving the first dose of study drug.
- In the case where the MRI is delayed for scheduling or other issues, or a repeat MRI is required because of scan quality issues, a repeat hematology assessment should be completed 2 to 7 days prior to the planned Day 1.
- Distribution of modified MFSAF v2.0 diary. Subjects will be issued a hand-held device, and will complete the diary questions each night beginning on Day -7 up to the Week 24 Visit. Subjects will be instructed to place the device on the docking station (also provided), for automatic data transmittal each night after completing the questions. Subjects will be instructed to leave the device in the docking station when not answering the questions so that the unit remains fully charged. Subjects will receive training on the device by study site staff prior to leaving the site. Subjects will bring the device with them to Study Visits on Day 1, Week 4, Week 8, Week 12, Week 16 and Week 20 so that the device charging can be verified, and to download accumulated data. The device will then be returned to the subject at these same visits for continued use each night. Subjects will return the device and the docking station for the final time at the Week 24 Visit, so that all data can be archived. All subjects will complete the diary through Week 24.
- Subjects will be given a reminder card with the date and time of the Day 1 visit. Subjects will be reminded to arrive for the study visit after an overnight fast of at least 8 hours or since midnight.

9.2. Core Treatment Phase

Refer to [Table 3](#), Study Visit Assessments and [Table 4](#), Scheduled Laboratory Assessments for procedures to be performed at on-study visits and laboratory-only visits. Subjects do not need to come in for study visits in the fasted state except for baseline, Day 1, Week 4, and Week 24, when they should arrive for the visit after an overnight fast of at least 8 hours or since midnight.

The site must ensure that the subject is instructed NOT to take the dose of study drug on the day of the Week 4 study visit, as study drug will be administered in the clinic at that visit [REDACTED]. [REDACTED] Reminder cards will be used to send home with subjects to state upcoming visit scheduling, and to record the time subjects took their last dose prior to each visit. Use of the reminder cards by site staff is mandatory, and they will be retained in the subject's records.

The procedures are summarized as follows:

Day 1

- Record adverse events
- Update concomitant medications

- Complete a targeted physical examination
- Administration of first dose of ruxolitinib, exact time recorded on eCRF.

█ [REDACTED]

█ [REDACTED]

█ [REDACTED]

█ [REDACTED]

- Study drug will be dispensed via IVRS.
- MFSAF v2.0 diary collection, data downloading and return to subject.
- Dispense reminder card to record time of dose on the day prior to Week 4 visit, and to remind subject NOT to take their morning dose the day of the Week 4 visit, to arrive for the visit after an overnight fast of at least 8 hours or since midnight, and to provide visit scheduling details.

Weeks 1, 2, 3, 5, 6, 7, 10, 14, and 18 (± 3 days)

- Subjects will go to the study site laboratory, or a local laboratory for blood draws for hematology assessments.
- The laboratory visits at Week 14 and Week 18 may be skipped for subjects who do not increase their dose at Week 12 or Week 16, and who have maintained platelet counts $> 75 \times 10^9/L$ since the last hematology assessment. Additional, twice-weekly laboratory-only visits to collect hematology lab samples will be required if platelet count falls below $35 \times 10^9/L$.

Week 4 (± 5 days)

- Review concomitant medications.
- Review transfusion status.
- Record adverse events.
- Complete a targeted physical examination.
- Measurement of spleen length below the costal margin by palpation.
- Vital signs.
- Complete PGIC question ([Appendix 5](#)).
- ECOG status assessment.

█ [REDACTED]

- Reminder card will be distributed to record the time of the dose taken the day of the Week 8 visit, to record the time of the meal prior to the visit, and to provide visit scheduling details.

- Dispense study drug via IVRS.
- Perform study drug accountability assessment.
- MFSAF v2.0 diary collection, data downloading and return to subject.
- Blood sampling for the following laboratory tests (see [Appendix 4](#)):
 - Serum chemistry tests
 - Hematology
 - Lipid panel

█ [REDACTED]

█ [REDACTED]

█ [REDACTED]

- Administration of ruxolitinib, exact time recorded on eCRF.

█ [REDACTED]

█ [REDACTED]

█ [REDACTED]

Week 8 (± 5 days)

- Review concomitant medications.
- Review transfusion status.
- Record adverse events.
- Complete a targeted physical examination
- Measurement of spleen length below the costal margin by palpation.
- Vital signs.
- Complete PGIC question ([Appendix 5](#)).
- ECOG status assessment.
- Dispense reminder card with Week 12 visit scheduling details.
- Dispense study drug via IVRS.
- Perform study drug accountability assessment.
- MFSAF v2.0 diary collection, data downloading and return to subject.
- Blood sampling for the following laboratory tests (see [Appendix 4](#)):
 - Serum chemistry tests
 - Hematology
 - Sample for plasma level of ruxolitinib (prior meal/dose times will be recorded)

Week 12 (\pm 5 days)

- Review concomitant medications.
- Review transfusion status.
- Record adverse events.
- Complete a targeted physical examination.
- Measurement of spleen length below the costal margin by palpation.
- Vital signs.
- Complete PGIC question ([Appendix 5](#)).
- ECOG status assessment.

█ [REDACTED]

- Reminder card will be distributed with Week 16 visit scheduling details.
 - MFSAF v2.0 diary collection, data downloading and return to subject.
 - Dispense study drug via IVRS.
 - Perform study drug accountability assessment.
 - Blood sampling for the following laboratory tests (see [Appendix 4](#)):
 - Serum chemistry tests
 - Hematology
 - Lipid panel
- █ [REDACTED]
- Coagulation panel

Week 16 (\pm 5 days)

- Review concomitant medications.
- Review transfusion status.
- Record adverse events.
- Complete targeted physical examination.
- Measurement of spleen length below the costal margin by palpation.
- Vital signs.
- Complete PGIC question ([Appendix 5](#)).
- ECOG status assessment.
- Reminder card will be distributed with Week 20 visit scheduling details.
- MFSAF v2.0 diary collection, data downloading and return to subject.

- Dispense study drug via IVRS.
- Perform study drug accountability assessment.
- Blood sampling for the following laboratory tests (see [Appendix 4](#)):
 - Serum chemistry tests
 - Hematology

Week 20 (± 5 days)

- Review concomitant medications.
- Review transfusion status.
- Record adverse events.
- Complete targeted physical examination.
- Measurement of spleen length below the costal margin by palpation.
- Vital signs.
- Complete PGIC question ([Appendix 5](#)).
- ECOG status assessment.
- Reminder card will be distributed to remind subjects to arrive for the Week 24 visit after an overnight fast of at least 8 hours or since midnight, and with Week 24 visit scheduling details.
- MFSAF v2.0 diary collection, data downloading and return to subject.
- Dispense study drug via IVRS.
- Perform study drug accountability assessment.
- Blood sampling for the following laboratory tests (see [Appendix 4](#)):
 - Serum chemistry tests
 - Hematology

Week 24 (± 5 days)

- Review concomitant medications.
- Review transfusion status.
- Record adverse events.
- Perform comprehensive physical examination.
- Measurement of spleen length below the costal margin by palpation.
- Vital signs.
- MRI (or CT scan in applicable subjects).
- Complete PGIC question ([Appendix 5](#)).

- ECOG status assessment.
- [REDACTED].
- Collect MFSAF v2.0 diary and all cords and charging stations.
- Dispense reminder card for subsequent visit scheduling, if subject will continue to receive study drug.
- Dispense study drug via IVRS if subject will continue to receive study drug.
- Perform study drug accountability assessment.
- Blood sampling for the following laboratory tests (see [Appendix 4](#)):
 - Serum chemistry tests
 - Hematology
 - Coagulation tests
 - Lipid panel
- [REDACTED]
- [REDACTED]
- [REDACTED]

9.3. Extended Treatment Phase

Visits will occur every 12 weeks (eg, Weeks 36, 48, 60, 72, 84, 96, 108, 120, 132, 144, and 156) beginning with Week 36 (± 5 days). Subjects will have laboratory-only visits to collect hematology samples 6 weeks after the Week 24 visit (eg, Week 30), then after **each** extended treatment phase visit (eg, Weeks 42, 54, 66, 78, 90, 102, 114, 126, 138, and 150). Additional hematology assessments will be required if the subject has a dose modification or as clinically indicated.

The following procedures will be performed every 12 weeks:

- Review concomitant medications.
- Review transfusion status.
- Record adverse events.
- Measurement of spleen length below the costal margin by palpation.
- Perform comprehensive physical examination.
- Vital signs.
- Complete PGIC question ([Appendix 5](#)).
- ECOG status assessment.
- [REDACTED].
- Reminder card will be distributed with subsequent visit scheduling details.

- Dispense study drug via IVRS.
- Perform study drug accountability assessment.
- Blood sampling for the following laboratory tests (see [Appendix 4](#)):
 - Serum chemistry tests
 - Hematology
 - Lipid panel
 - [REDACTED]
 - Coagulation panel

Week 156 (± 5 days)

- Review concomitant medications.
- Review transfusion status.
- Record adverse events.
- Perform comprehensive physical examination.
- Measurement of spleen length below the costal margin by palpation.
- Vital signs.
- Complete PGIC question ([Appendix 5](#)).
- ECOG status assessment.
- [REDACTED].
- Update subject status in IVRS.
- Perform study drug accountability assessment.
- Blood sampling for the following laboratory tests (see [Appendix 4](#)):
 - Serum chemistry tests
 - Hematology
 - Coagulation tests
 - Lipid panel

■ [REDACTED]

9.4. End of Treatment (± 5 days)

If a decision is made that the subject will withdraw from study participation, the end-of-treatment visit (EOT) should be conducted. If the EOT Visit coincides with a regular study visit, the end-of-treatment evaluations will supersede those of that scheduled visit, the data should be entered in the end of treatment visit in the CRF. The subject should be encouraged to return for the follow-up visit. The following will be performed:

- Review concomitant medications.
- Review transfusion status.
- Record adverse events.
- Perform complete physical examination.
- Measurement of spleen length below the costal margin by palpation.
- Vital signs.
- MRI (or CT scan in applicable subjects) should only be performed at the EOT visit if the subject discontinues treatment **prior** to Week 24.
- Complete PGIC question ([Appendix 5](#)).
- ECOG status assessment.
- Perform study drug accountability assessment.
- Blood sampling for the following laboratory tests (see [Appendix 4](#)):
 - Serum chemistry tests
 - Hematology
 - Coagulation tests
 - Lipid panel
- 
- Contact IVRS to register subject discontinuation.

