| 
Overall Study Design:
 
This is an open label study of ruxolitinib in patients with PMF, PPV-MF, and PET-MF. The study is comprised of 4 phases:
 
 
 Screening:	Up to 21 days	
 
 Baseline:	Exactly 7 days	
 
 Core Treatment Phase:	24 weeks	
 
 Extended Treatment Phase:	132 weeks; subjects receiving benefit will continue ruxolitinib treatment until Week 156	
 
 Follow-up Phase:	All subjects will be followed for safety (eg, reporting of AEs and serious AEs) for 30 to 37 days after the last dose of study drug is administered	
 
 | | Screening: | Up to 21 days | Baseline: | Exactly 7 days | Core Treatment Phase: | 24 weeks | Extended Treatment Phase: | 132 weeks; subjects receiving benefit will continue ruxolitinib treatment until Week 156 | Follow-up Phase: | All subjects will be followed for safety (eg, reporting of AEs and serious AEs) for 30 to 37 days after the last dose of study drug is administered |
| Screening: | Up to 21 days | | | | | | | | | | |
| Baseline: | Exactly 7 days | | | | | | | | | | |
| Core Treatment Phase: | 24 weeks | | | | | | | | | | |
| Extended Treatment Phase: | 132 weeks; subjects receiving benefit will continue ruxolitinib treatment until Week 156 | | | | | | | | | | |
| Follow-up Phase: | All subjects will be followed for safety (eg, reporting of AEs and serious AEs) for 30 to 37 days after the last dose of study drug is administered | | | | | | | | | | |

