7. INVESTIGATIONAL PLAN

7.1. Overall Study Design

This is an open label study of ruxolitinib in patients with PMF, PPV-MF, and PET-MF. The study is comprised of 4 phases:

| | |
|----------------------------------|--|
| Screening: | Up to 21 days |
| Baseline: | Exactly 7 days |
| Core Treatment Phase: | 24 weeks |
| Extended Treatment Phase: | 132 weeks; subjects receiving benefit will continue ruxolitinib treatment until Week 156 |
| Follow-up Phase: | All subjects will be followed for safety (eg, reporting of AEs and SAEs) for 30 to 37 days after the last dose of study drug is administered |

Core Treatment Phase:

During the core treatment phase, there will be study visits and laboratory-only visits. Subjects will have a regularly scheduled study visit at screening, baseline, Day 1, Week 4, Week 8, Week 12, Week 16, Week 20 and Week 24, where blood samples, assessments, spleen measurements, etc. will be obtained. All hematology labs and coagulation parameters will be analyzed by local laboratories. Serum chemistries, serology, and lipid panel will be analyzed by a central laboratory.

Subjects will have laboratory-only visits to collect hematology lab samples at Week 1, Week 2, Week 3, Week 5, Week 6, Week 7, Week 10, Week 14, and Week 18. The laboratory visits at Week 14 and Week 18 may be skipped for subjects who do not increase their dose at Week 12 or Week 16, and who have maintained platelet counts $> 75 \times 10^9/L$ since the last hematology assessment. Additional, at least weekly laboratory-only visits to collect hematology lab samples will be required if platelet count falls below $35 \times 10^9/L$; more frequent monitoring is recommended if counts fall below $25 \times 10^9/L$. These laboratory visits can occur at the study site laboratory, or any local laboratory that can provide the data and appropriate certificates and normal laboratory ranges to the study site for review for subject management in a timely fashion.

Subjects will have an MRI of the upper and lower abdomen and pelvis to determine the spleen volume at baseline and Week 24. A CT scan will be substituted for subjects who are not candidates for MRI, or when MRI is not readily available. Patients Global Impression of Change (PGIC) questionnaire will be completed monthly. Measurement of spleen length below the left costal margin will be measured by palpation at each study visit.

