- ^h The first MRI may be delayed for up to 2 weeks because of scheduling or other issues at the clinic site, but must be completed within 56 days, maximum from the start of the original Screening Visit date, and this must occur prior to the subject receiving the first dose of study drug.
- ⁱ An MRI should be conducted at the end of treatment visit **only** if treatment was is discontinued prior to Week 24.
- ^k [REDACTED]
- ^k Reminder cards will be sent home with subjects to state upcoming visit scheduling, and to record the time subjects took their last dose of study drug prior to each visit.
- ^l On Day 1, the first dose of ruxolitinib will be administered to the subject in a fasted state at the site and the exact time of administration will be recorded on the eCRF.
- ^m Subject should be instructed NOT to take the morning dose of study drug on the day of the Week 4 study visit, as study drug will be administered to the subject in a fasted state at the clinic.

Table 4: Table of Laboratory Assessments

| Study Phase | Screening & Baseline | | Core Treatment Phase | | | | | | | Extended Treatment Phase | | End of Treatment & Follow-Up | |
|--|----------------------|-----------------------|----------------------|--|---------------------|----------|----------|-----------------|----------------------|------------------------------|---------------------------|---|--|
| | Screening | Baseline ^a | Day 1 ^a | Lab Only Visits Weeks 1,2,3,5,6,7,10,14,18 | Week 4 ^a | Week 8 | Week 12 | Weeks 16 and 20 | Week 24 ^a | Lab Only Visits ^b | Study Visits ^b | End of Treatment or Early Termination Visit (EOT) | Follow-Up 30-37 days After Last Dose of Study Drug |
| Evaluation/window | Day -28 to -8 | Day -7 to -1 | Day 1 | ± 3 days | ± 5 days | ± 5 days | ± 5 days | ± 5 days | ± 5 days | ± 5 days | ± 5 days | ± 5 days | ± 5 days |
| Serum Chemistry | X | X ^c | | | X | X | X | X | X | | X | X | X |
| Hematology | X | X ^c | | X ^d | X | X | X | X | X | X | X | X | X |
| Coagulation panel | X | X | | | | | X | | X | | X | X | |
| Lipid Panel | | X | | | X | | X | | X | | X | X | |
| Serum Pregnancy Test (childbearing females only) | X | | | | | | | | | | | | |
| Serology for HIV, HBV, HCV | X | | | | | | | | | | | | |

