10.4. Efficacy Assessments

- **Imaging.** The primary measure of spleen size will be by MRI (or CT scan in applicable subjects). MRI of the upper and lower abdomen and pelvis will be performed at baseline and Week 24. MRI will be performed with a body coil because the objective is to measure organ volume, not to find very small lesions. MRIs will be read initially by local radiologists who will assess the scan for quality, and send all scans (MRI or CT) to the central imaging laboratory the same day, if at all possible. The scans from an individual subject will be read by a central reader. Spleen and liver volume will be obtained by outlining the circumference of the organ and

determining the volume using the validated technique of least squares. The MRI will not determine spleen length below the costal margin, as there are no validated approaches for determining this measurement. Procedure specific training for scanning and image capture will be provided by the Vendor.

[figure not shown]
[figure not shown]
[figure not shown]
MRI is the preferred method for obtaining spleen volume data. However, CT scans may be performed at the visits where MRI is designated if the subject is not a candidate for MRI (because of the presence of metal clips in the body, or because of claustrophobia, for example), or if MRI is not readily available. CT scans will be similarly processed by the same central laboratory as used for MRIs. Procedure specific training for scanning and image capture will be provided by the Vendor. NOTE: The same method (MRI versus CT) must be used for both visits for a given subject unless a new contraindication to the use of MRI (eg, pacemaker insertion) occurs.

[figure not shown]
[figure not shown]
- **Spleen length.** Spleen length will be assessed by manual palpation as outlined in [Table 3](#). Investigators will be provided with a soft centimeter ruler so that palpable spleen length is measured in centimeters and not in finger breadths. The edge of the spleen shall be determined by palpation, and measured in centimeters, using a soft ruler, from the costal margin to the point of greatest splenic protrusion. Spleen length must be recorded on the eCRF.

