#### **5.6. Day 1, Study Day, and Study Time Points**

Day 1 is the date of first dose of study medication.

The study day at a visit/reporting date will be calculated by the visit/reporting Date – Day 1 + 1. This study day will be subtracted by 1 if it is less than or equal to zero, so that a study day of zero will never occur. A study day of -1 indicates 1 day prior to Day 1.

Other study time points will use nominal weeks, such as Weeks 4, 8, 12, etc, according to the Schedules of Assessments (see [Table 2](#) and [Table 3](#)), as recorded on the CRF, regardless of the actual time windows these visits fall into, unless otherwise stated. This is especially true for analyses such as laboratory values and vital sign values where by-study-week summaries are to be generated, as well as for spleen palpation length over time summaries.

Exceptions to the statements about study time points described above include (but are not limited to) spleen volume at Week 24 (see [Section 5.9.1](#)), total symptom score at several major study time points (see [Section 5.6](#)), and final titrated dose level (see [Section 5.9.3.1](#)).

Another exception is related to spleen palpation length analysis. Per study CRF design, if a subject's EOT Visit coincides with a scheduled visit, then in database, only EOT Visit data will be available. So when a subject has spleen palpation length data collected on an "EOT Visit" (or End of Extension Phase Visit, as appropriate and if applicable), an effort will be made to see if the data actually falls into a scheduled visit, such as Weeks 4, 8, 12, 16, 20, 24 (treatment phase), 36, 48, 60, etc (extension phase) by using the window of Week of scheduled visit\*7 ± 5 days.

Following the situation described above, if EOT data contain spleen volume measurements and the situation is not resolved by the time of database lock, then similar effort will be made by treating spleen volume data labeled from "EOT Visit" as data collected from unscheduled visit. See [Section 5.9.1](#) for how spleen volume data from unscheduled visits will be used in the analysis.

The situation described above is not an issue of importance to other variables such as laboratory values, since in analyses by time point, "EOT" will be one of the time points to be displayed.

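### Section 9.4 and the Table 3 EOT footnote conflict with the unconditional Week 24 MRI when a subject's end-of-treatment visit falls at Week 24, so a site could omit the first co-primary scan

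*Protocol*

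**What the plan says.** Two places in the protocol restrict the scan at the end-of-treatment (EOT) visit.

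- Section 9.4 covers coinciding visits: "If the EOT Visit coincides with a regular study visit, the end-of-treatment evaluations will supersede those of that scheduled visit". Its own procedure list says that the MRI or CT "should only be performed at the EOT visit if the subject discontinues treatment" before Week 24.
- The Table 3 footnote on the EOT column says "An MRI should be conducted at the end of treatment visit" only "if treatment was is discontinued prior to Week 24".

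Other places require the scan with no exception.

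- Section 7.1: "Subjects will have an MRI of the upper and lower abdomen and pelvis to determine the spleen volume at baseline and Week 24".
- Section 10.4: "MRI of the upper and lower abdomen and pelvis will be performed at baseline and Week 24".
- Section 9.2, Week 24 list: MRI or CT is an unconditional item. Only the reminder card and drug dispensing depend on whether the subject will go on taking drug.
- Table 3 has an unqualified entry for MRI in the Week 24 column.

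On who goes on after Week 24, the Synopsis and Section 7.1 say that "subjects receiving benefit will continue ruxolitinib treatment until Week 156".

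SAP Section 5.6 recognises the overlap: "if a subject's EOT Visit coincides with a scheduled visit, then in database, only EOT Visit data will be available". It treats a spleen volume labelled EOT as unscheduled data, and SAP Section 5.9.1 accepts unscheduled values from Day 141 to Day 175.

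**The concern.** Take a subject who uses study drug up to the Week 24 visit and stops there. The Week 24 visit is then also the EOT visit. Section 9.4 is the only text on coinciding visits, and it says that the EOT evaluations take over. The subject did not stop before Week 24, so the EOT list calls for no MRI. It also omits collection of the diary device, which the Week 24 list includes.

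The percent change in spleen volume at Week 24 is half of the first co-primary endpoint. Under protocol Section 12.2.1 and SAP Section 5.4.2, its test must succeed before the symptom-score correlation is tested formally. A scan missed at Week 24 cannot be obtained later. Because those who continue are described as subjects receiving benefit, scans lost through this rule could come more often from poor responders. The correlation and the mean percent change would then rest on a set tilted towards responders.

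**Working it through.** **Step 1. Which instruction applies to a subject who stops at Week 24?**

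| Place | Instruction on the scan |
|---|---|
| 9.4, coinciding visits | EOT evaluations replace the scheduled ones |
| 9.4, EOT list, and Table 3 EOT footnote | MRI only if treatment stopped before Week 24, so none here |
| 7.1, 10.4, Table 3 Week 24 column | MRI at Week 24, no exception |
| 9.2, Week 24 list | MRI unconditional, on a list that foresees subjects who will not continue |

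The first two rows give no scan and the last two give a scan. No text says which prevails.

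**Step 2. Can the SAP repair a loss?** Week 24 ± 5 days is Day 168 ± 5, or Day 163 to 173. That lies inside Day 141 to 175, so a scan taken at the visit and filed as EOT is usable. A scan never taken is not. The multiple-imputation analysis in SAP Section 7.1 is optional, and its model is left to be added in the shell for Table 14.2.1.3.

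**Step 3. The plan's own figures** (protocol Section 12.4: n = 150, two-sided 5%, SD 19%).

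- Critical correlation: r_crit = t/√(n − 2 + t²) = 0.160. The plan states 0.16.
- Power = Φ{[atanh(r) + r/(2(n − 1)) − atanh(r_crit)]·√(n − 3)} = 96.4%, 87.4% and 69.3% at r = 0.30, 0.25 and 0.20. The plan states 96%, 87% and 69%.
- Half-length of the 95% interval: 1.96 × 19/√150 = 3.04. The plan states about 3.

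All reproduce.

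**Step 4. Size of a loss, under assumptions.** The share f stopping at Week 24 is not in the documents, so take 5%, 10% and 20% of 150: about 8, 15 and 30 scans, leaving 142, 135 and 120. The 8 of 50 subjects (16%) reported at the interim analysis as stopping before Week 24 are a different group, for whom the EOT scan is ordered.

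*Loss unrelated to response.* Only n falls.

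| True r | n = 142 | n = 135 | n = 120 |
|---|---|---|---|
| 0.30 | 95.6% | 94.6% | 91.9% |
| 0.25 | 85.6% | 83.7% | 79.2% |
| 0.20 | 66.9% | 64.7% | 59.5% |

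*Worst-case selection.* Assume that every such scan is omitted, that those lost are exactly the worst responders, and that dose and response are bivariate normal. With z the upper-f normal quantile and λ = φ(z)/(1 − f), the mean shifts by 19λ. The retained variance of response, as a fraction of the full variance, is s² = 1 − zλ − λ². The correlation becomes r·s/√(1 − r²(1 − s²)).

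| f | z | λ | Mean shift 19λ | s² | Observed size of r when the true size is 0.30 | Power |
|---|---|---|---|---|---|---|
| 5% | 1.645 | 0.1086 | 2.06 | 0.810 | 0.27 | 91% |
| 10% | 1.282 | 0.1950 | 3.70 | 0.712 | 0.26 | 86% |
| 20% | 0.842 | 0.3500 | 6.65 | 0.583 | 0.23 | 73% |

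If stopping correlates only 0.5 with response, the mean shifts halve to about 1.0, 1.9 and 3.3 points.

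**The case against.** The strongest reply is that the documents, read as a whole, intend the scan to be done. Sections 7.1 and 10.4 and Table 3 require it for all. The Week 24 list makes two items conditional on continuing, which would be pointless if the list did not apply to subjects who stop there, and it leaves the MRI unconditional. The limit in 9.4 can be read as sparing a second scan for those who already had one at Week 24. SAP Section 5.6 plans for EOT-labelled spleen volumes. In the SAP's own schedule, written against Amendment 1, the EOT column has no MRI, so such a value is most naturally a Week 24 scan filed as EOT. The diary is little exposed: data are transmitted nightly, and Sections 9.1.2 and 10.5 require the device back at Week 24.

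Most of this stands. It shows what was probably meant, but it does not remove the contradiction. The sentence in 9.4 concerns evaluations and deals with data entry in a separate clause, so reading it as a filing rule only is not secure.

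A reader might also infer that the subjects affected are those without benefit. The documents do not go that far. There is no benefit criterion or Week 24 stopping rule, and lack of benefit is not among the mandatory withdrawal reasons in Section 8.7.1. Subjects may stop at Week 24 for other reasons, or decide after that visit and its scan. Those who stop shortly before Week 24 do get the EOT scan.

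**Conclusion.** The protocol contradicts itself on whether the first co-primary scan is taken when the EOT visit coincides with Week 24. A site that follows 9.4 literally could omit it, and because continuation is tied to benefit, the loss could be related to response.

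The stronger reading, that the plan drops the scan in these subjects, is not supported: several sections order the scan without exception, and the SAP expects some EOT-labelled values.

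The size is unknown. Under the assumed 5%, 10% and 20% with worst-case selection, the mean percent reduction would be overstated by about 2.1, 3.7 and 6.6 points. Power at a true correlation of 0.30 would fall from 96% to about 91%, 86% and 73%. With no selection, power stays near 96%, 95% and 92%. The share, the omission at every site and the degree of selection are all assumptions. The responder tables are less exposed, because the shell for SAP Table 14.2.2.2 lists discontinuation and missing data as reasons for not reaching the threshold.

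This is an inconsistency that should be fixed, not a demonstrated loss of the endpoint.

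**What to change.** Reconcile Sections 7.1, 9.2, 9.4 and 10.4 with the Table 3 EOT footnote. State in 9.4 and in the footnote that when the EOT visit coincides with the Week 24 visit, the already planned Week 24 MRI or CT and the diary return are still performed.

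No SAP change is strictly needed, since Sections 5.6 and 5.9.1 already make an EOT-labelled scan usable from Day 141 to Day 175. A cross-reference would be enough.

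The cost is one sentence in each of two places in the protocol. No procedure is added, because the Week 24 scan is already planned for every subject.
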